### **8.2.5 Rationale for selection criteria**

The assignment of the patient to Tresiba® is decided in advance of this the protocol and as part of current practice. Hence, the prescription of Tresiba is clearly separated from the decision to include the patient in the study.

## 8.2.6 Flowchart

**\* The assignment of the patient to Tresiba® is not decided in advance by the protocol but falls within current practice and the prescription of Tresiba® is clearly separated from the decision to include the patient in the study.**

## 8.3 Variables

Details of all concomitant illnesses and medication must be recorded at trial entry (i.e. at the first visit (Visit 1)).

The information collected for each concomitant medication includes at a minimum, start date, stop date or continuing and indication. A clinically significant worsening of concomitant illness must be reported as an AE.

Definitions:

- Concomitant illness: any illness that is present at the start of the study.
- Concomitant medication: any medication other than Tresiba® and other anti-diabetic medications that is taken during the study.

- Confirmed hypoglycaemia: In normal physiology, symptoms of hypoglycaemia occur below a plasma glucose level of 3.1 mmol/L (56 mg/dL). Therefore, Novo Nordisk has included hypoglycaemia with plasma glucose levels below this cut-off point in the definition of confirmed hypoglycaemia.
- Confirmed hypoglycaemic episodes are defined as episodes that are severe (ie, an episode requiring assistance of another person to actively administer carbohydrate, glucagon, or other resuscitative actions) and/or biochemically confirmed by a plasma glucose value of <3.1 mmol/L (56 mg/dL), with or without symptoms consistent with hypoglycaemia

### 8.3.1 Assessments for safety and efficacy

	Visit 1 (0 weeks)	Visit 2 (3 months ± 2 weeks)	Visit 3 (6 months ± 2 weeks)	Visit 4 (1 year ± 2 weeks)
Patient informed consent	X			
Patient eligibility	X			
Early termination		X	X	X
Demographic data 	X			
Diabetes history	X			
Confirmed Hypoglycaemic events  since last visit		X	X	X
Most recent HbA1c value and date of measurement (if available) 	X	X	X	X
Most recent FPG/FBG value and date of measurement (if available) 	X	X	X	X
Diabetes treatment before the PMS/PASS study was initiated	X			
Diabetes treatment during the PMS/PASS study		X	X	X
Concomitant medications	X	X	X	X
AEs/SAEs/ADRs/SADRs 		X	X	X

 Including body weight, height, waist and hip circumference, systolic and diastolic blood pressure measured in sitting posture (if available)

 Confirmed hypoglycaemia: In normal physiology, symptoms of hypoglycaemia occur below a plasma glucose level of 3.1 mmol/L (56 mg/dL). Therefore, Novo Nordisk has included hypoglycaemia with plasma glucose levels below this cut-off point in the definition of confirmed hypoglycaemia.

Confirmed hypoglycaemic episodes are defined as episodes that are severe (ie, an episode requiring assistance of another person to actively administer carbohydrate, glucagon, or other resuscitative actions) and/or biochemically confirmed by a plasma glucose value of <3.1 mmol/L (56 mg/dL), with or without symptoms consistent with hypoglycaemia.

 For visit 1, the term recent means “over the past 4 weeks before starting on insulin degludec”.

 Each AE/SAE will be recorded on a separate AE form according to existing reporting procedures. If the AE is serious then a Safety Information Form will also be completed and the sponsor or their designee notified within the specified period. Severe hypoglycaemic episodes (according to definition in footnote #2) always qualify for AE/SAE reporting.

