## Secondary efficacy endpoints

- Change from baseline in HbA1c after 1 year of treatment
- Change from baseline in FPG after 1 year of treatment
- Incidence of confirmed hypoglycaemia during 1 year of treatment

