#### 8.1.3 Treatment of patients

Patients with diabetes mellitus requiring insulin therapy who qualify for starting treatment with Tresiba® based on the clinical judgment by their treating physician will be treated with Tresiba® according to routine clinical practice at the discretion of the treating physician. The assignment of the patient to Tresiba® is not decided in advance by the protocol but falls within current practice and the prescription of the medicine is clearly separated from the decision to include the patient in the study. Tresiba® will be prescribed by the physician under normal clinical practice conditions and will be obtained/ purchased from the chemist based on physician prescription. The physician will determine the starting dose, as well as later changes to dose, if any. Tresiba® should be used in accordance with the Indian package insert

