### **8.2.3 Exclusion criteria**

1. Known or suspected allergy to Tresiba®, the active substance or any of the excipients
2. Previous participation in this study
3. Mental incapacity, unwillingness or language barriers precluding adequate understanding or cooperation.
4. Patients who are or have previously been on Tresiba® therapy.
5. Patients who are participating in other studies or clinical trials
6. Patients who are pregnant, breast feeding or have the intention of becoming pregnant within the following 12 months

[figure not shown]

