### **Visits 2, 3 & 4**

The physician will gather the following information from either the patient's medical record, patient recall, and/or the patient's SMBG diary:

- All AEs/SAEs/ADRs/SADRs reported by the patient since last visit
- Reasons for early termination (lost to follow-up, ADR, meeting withdrawal criteria), if applicable
- Number of all confirmed hypoglycaemic episodes experienced since last visit

- Number of all episodes of severe hypoglycaemia experienced since last visit
- Date and value of most recent HbA1c since last visit
- Most recent FPG/FBG value and date of measurement since last visit
- DM treatment prescribed since the last visit
  - Change in Tresiba® treatment (date of change and the prescribed dose)
  - Any other anti-diabetic treatment (metformin, sulphonylureas, metiglinides, alpha-glucosidase inhibitors, thiazolidinediones, DPP-IV inhibitor, basal insulin, premix insulin, bolus insulin, etc)
- Concomitant medications

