### **8.7.2 Statistical methods**

The primary endpoint will be summarized using descriptive statistics by SOC and preferred term showing number of subject with events, number of events, incidence rate and rate per 100 PYE. Exposure to be used in the calculation in rate should be defined as the timeframe from time of first Tresiba® dose to last contact in this PMS/PASS trial. All secondary endpoints related to AEs (ADR/SADR/SAEs) will be presented in a similar way.

These endpoints will also be presented by the severity grade.

Hypoglycaemic episodes will be summarised in a similar way presenting confirmed and severe episodes separately.

The continuous variables HbA1c and FPG, demographic data will be summarized with descriptive statistics (N, N miss (number of missing values), mean, standard deviation, and median). Baseline, end of trial values and change from baseline values will be presented. Missing values will be subject to last observation carried forward (LOCF)

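### At Visit 2 confirmed hypoglycaemia is counted from Visit 1, but exposure starts at the first Tresiba dose, so non-severe episodes before that dose can enter the rate and cannot be removed later

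*Protocol*

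**What the plan says.** **Counting window.** The table in Protocol 8.3.1 has a row for "Confirmed Hypoglycaemic events 2 since last visit", marked at Visits 2, 3 and 4. The list for those visits in 8.4.1 asks for "Number of all confirmed hypoglycaemic episodes experienced since last visit" and, on a separate line, "Number of all episodes of severe hypoglycaemia experienced since last visit". Both are numbers per interval. No onset date is listed for a confirmed episode.

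**Endpoint.** Section 7.3 gives "Incidence of confirmed hypoglycaemia during 1 year of treatment" as a secondary efficacy endpoint.

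**Denominator.** Section 8.7.2 says that exposure for the rates is "defined as the timeframe from time of first Tresiba ® dose to last contact". It then has hypoglycaemic episodes summarised in the same manner as adverse events, which includes a rate per 100 patient-years of exposure.

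**Entry and supply.** Inclusion criterion 2 (8.2.2) takes patients who are due to start Tresiba. Exclusion criterion 4 (8.2.3) bars "Patients who are or have previously been on Tresiba ® therapy". Under 8.1.3 the pen is "obtained/ purchased from the chemist based on physician prescription". The Tresiba start date is among the items recorded at Visit 1 (8.4.1).

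**Severe episodes.** Footnote 4 of the table adds: "Severe hypoglycaemic episodes (according to definition in footnote #2) always qualify for AE/SAE reporting".

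**The concern.** The numerator and the denominator of the hypoglycaemia rate have different starting points. At Visit 2 the last visit is Visit 1, so the count opens at Visit 1. Person-time opens at the first dose. The entry criteria put that dose on or after Visit 1 and never before it, so any mismatch works in one direction: it adds time to the count and none to the exposure. It can also add patients to the number with at least one episode, if their only episode came before the first dose.

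The study has no comparator (8.1.2), so the absolute rate and incidence are themselves the result, and no parallel arm carries the same error. Hypoglycaemia is one of the eight listed reasons for starting Tresiba (8.4.1, Visit 1). For such patients the rate before the first dose may exceed the rate afterwards.

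This is a rule about what is collected, so an analysis plan could not repair it for non-severe episodes. An on-treatment rule needs a date for each episode, and the listed items supply only a number.

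**Working it through.** **The protocol's own figure.** There is none on this point. The protocol states neither the time from Visit 1 to first dose nor a hypoglycaemia rate before or after the switch. The figures in 8.5 concern detection of rare events and do not bear on it.

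**Which patients contribute.** Confirmed hypoglycaemia is summarised on the Efficacy Analysis Set, a subset of those with at least one dose (8.7.1). Patients who never start do not enter. The issue is confined to treated patients who start after Visit 1.

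**Set-up.** Let Visit 1 be day 0, the first dose day *g*, and last contact day 365. Let the episode rate on Tresiba be λ per day and the rate before the first dose RR × λ.

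- Episodes counted: λ × [RR × g + (365 − g)]
- Exposure used: 365 − g
- Reported rate divided by true on-treatment rate: 1 + RR × g/(365 − g)

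The relative overstatement is RR × g/(365 − g). It is zero when g = 0 and positive for any g above 0 and any RR above 0.

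**Numbers.** Both g and RR are assumptions, because the protocol gives neither. At RR = 1: 3/362 = 0.8%, 7/358 = 2.0%, 14/351 = 4.0%, 28/337 = 8.3%.

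| Gap g (days) | RR = 0.5 | RR = 1 | RR = 2 |
|---|---|---|---|
| 0 | 0% | 0% | 0% |
| 3 | 0.4% | 0.8% | 1.7% |
| 7 | 1.0% | 2.0% | 3.9% |
| 14 | 2.0% | 4.0% | 8.0% |
| 28 | 4.2% | 8.3% | 16.6% |

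The table takes the same gap for every patient. If half wait 14 days and half start on the day of Visit 1, then at RR = 1 the overstatement is (0.5 × 14)/(0.5 × 351 + 0.5 × 365) = 7/358 = 2.0%. That equals the figure for a uniform gap of 7 days, so the average gap is what counts.

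**Visit 2 interval alone.** With 91 days from Visit 1 to Visit 2, the overstatement at RR = 1 is g/(91 − g): 7/84 = 8.3% and 14/77 = 18.2%. This would matter only if that interval were reported by itself, or for patients who leave at Visit 2.

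**Can the episodes be separated afterwards?** The recorded start date gives the length of the gap but not which episodes fell in it. Patients are asked to keep a diary, but its transfer to the CRF is conditional on availability (8.4.1), and the item to be filled in is a count. For non-severe confirmed episodes the answer on the listed items is therefore no.

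**The case against.** **No delay is stated.** Visit 1 is labelled 0 weeks in 8.3.1. The Tresiba start date and the treatment prescribed are Visit 1 items, and the schedule runs to one year, matching a year of treatment. All of this fits a first dose on or near the day of Visit 1. Purchase from a chemist makes a delay possible but does not show one. This stands, and it limits the point to what can happen. A reader might infer that episodes on the previous therapy are in fact being charged to Tresiba; the documents do not support that.

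**Severe episodes are largely protected.** A reader might infer from footnote 4 that severe episodes before the first dose also become Tresiba events. Section 10.2.3 defines an adverse event as occurring in a patient who has been given the product. Each event has its own form from start to resolution (10.3), so severe episodes can probably be separated by onset. Inclusion criterion 1 also allows severe hypoglycaemia before the start of Tresiba to serve as baseline data. This stands, so footnote 4 needs no change.

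**The effect is small.** The study is descriptive with no formal testing (8.7), and the counts may rest on patient recall. One could reach much larger percentages by giving every patient a long wait and a several-fold higher earlier rate, but nothing in the protocol supports that combination. Section 8.1.4 describes adding insulin when other therapy fails, so some patients may have had a low earlier rate. This stands as to size. It does not remove the mismatch, which is one-directional and, for non-severe episodes, cannot be undone once the data are collected.

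**An analysis plan may exist.** It could define an on-treatment period, but it could not date episodes recorded only as numbers.

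**Conclusion.** The point holds in a limited form. As worded, the Visit 2 count starts at Visit 1, the exposure starts at the first dose, and nothing limits the interval between them. Any non-severe confirmed episode in that interval can be counted without matching exposure and cannot be taken out later.

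The bias is zero for patients who start on the day of Visit 1. Under assumed gaps of 3 to 14 days for all patients and equal rates before and after the start, the one-year rate is overstated by about 0.8% to 4%. At 14 days it is about 2% if the earlier rate was half the later one and about 8% if it was twice. These sizes rest entirely on the assumed gaps and rate ratios.

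The conclusions of a descriptive study are unlikely to turn on an error of this size. It is worth correcting because the correction is nearly free before data collection and unavailable for non-severe episodes afterwards.

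**What to change.** In the hypoglycaemia row of 8.3.1 and in the list for Visits 2, 3 and 4 in 8.4.1, word the Visit 2 item as *since the first Tresiba dose*. Keep the present wording for Visits 3 and 4. The count of severe episodes in 8.4.1 should take the same start at Visit 2, so that it remains a subset of the confirmed count. Recording an onset date for each confirmed episode would also work, at more burden to sites.

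The cost is wording in two places and one CRF label at Visit 2. No test, visit or patient is added, and the Tresiba start date is already collected. The Visit 2 answer would still depend on recall or the diary, as it does now. The reported rate may fall slightly.

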### **8.3.2 Other assessments**

Patients will not undergo any additional testing or assessments for the purposes of this study.

## **8.4 Data sources**

The PMS/PASS study is conducted in a real-life setting and without extensive monitoring of the data collected. Hence there is a risk that complete data stated in the protocol are not always collected from all patients. However data includes routine clinical measurements which can be recorded and analyzed for measuring safety and efficacy of Tresiba®

### **8.4.1 Visit procedures**

In agreement with its observational nature, there are no interventions in standard care for this study. Any procedure ordered by the physician during this study will be according to routine practice. The patient will not be called in for premature discontinuation or for a missed visit. The primary reason (adverse drug reaction or other) for discontinuation must be specified in the CRF. Patients will be instructed to maintain a diary to record AEs, hypoglycaemic episodes and concomitant medications, and these data will be entered into the paper CRF (If available). The patient must be asked about adverse events during each contact (visit or telephone) with the physician or study site staff. This may be done by posing a simple question such as “have you experienced any problems since the last contact?”

A patient who meets all inclusion criteria and none of exclusion criteria will be enrolled in the study and assigned a patient number. Patients enrolled in the study will be provided with contact address (es) and telephone number(s) of the physician and/or site staff.

### **Visit 1**

The physician will gather the following information from either the patient’s medical record, patient recall or patient’s diary (If available).

- Patient informed consent date

- Patient eligibility
- Demographic data:
  - Date of birth
  - Gender
  - Race
- Body measurements:
  - Weight
  - Height
  - Waist and hip circumference
  - Systolic and diastolic blood pressure measured in sitting posture
- DM history:
  - Date of diagnosis of DM
  - Type of diabetes (Type I or Type II)
  - Diabetic macro-vascular complications (peripheral vascular disease, coronary heart disease, stroke).
  - Diabetic micro-vascular complications (diabetic retinopathy, diabetic nephropathy, diabetes neuropathy)
- DM treatment before PMS/PASS study initiated (follow any physician recommended diet plan and exercise for diabetes management, metformin, sulphonylureas, metiglinides, alpha-glucosidase inhibitors, thiazolidinediones, DPP-IV inhibitor, basal insulin, premix insulin, bolus insulin, exenatide, liraglutide, etc).
- Most recent FPG/FBG value and date of measurement prior to starting insulin degludec treatment (if available)
- DM treatment prescribed during PMS/PASS study
- Reasons why decision was taken to start therapy with insulin degludec (increased HbA1c, increased FPG/FBG, increased PPBG/PPPG, side effects from previous therapy, hypoglycaemia, patient dissatisfaction with previous therapy, flexibility need, once-daily treatment need)
- Starting date of Tresiba® therapy
- Concomitant medications excluding diabetes medication

### **Visits 2, 3 & 4**

The physician will gather the following information from either the patient's medical record, patient recall, and/or the patient's SMBG diary:

- All AEs/SAEs/ADRs/SADRs reported by the patient since last visit
- Reasons for early termination (lost to follow-up, ADR, meeting withdrawal criteria), if applicable
- Number of all confirmed hypoglycaemic episodes experienced since last visit

- Number of all episodes of severe hypoglycaemia experienced since last visit
- Date and value of most recent HbA1c since last visit
- Most recent FPG/FBG value and date of measurement since last visit
- DM treatment prescribed since the last visit
  - Change in Tresiba® treatment (date of change and the prescribed dose)
  - Any other anti-diabetic treatment (metformin, sulphonylureas, metiglinides, alpha-glucosidase inhibitors, thiazolidinediones, DPP-IV inhibitor, basal insulin, premix insulin, bolus insulin, etc)
- Concomitant medications

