## 1 List of abbreviations

ADR	Adverse Drug Reaction
AE	Adverse Event
BMI	Body Mass Index
CRF	Case Report Form
CRO	Contract Research Organisation
CV	Curriculum Vitae
DCF	Data Clarification Form
EAS	Efficacy Analysis Set
EDC	Electronic Data Capture
ENCePP	European Network of Centres for Pharmacoepidemiology and Pharmacovigilance
FAS	Full Analysis Set
FBG	Fasting Blood Glucose
FPG	Fasting Plasma Glucose
GVP	Good Pharmacovigilance Practice
GPP	Good Pharmacoepidemiology Practice
HbA1c	Glycated Haemoglobin
ICF	Informed consent form
IEC	Independent Ethics Committee
IRB	Institutional Review Board
LAR	Legally Acceptable Representative
OAD	Oral anti-diabetic drugs
PASS	Post Authorisation Safety Study
PMS	Post Marketing Surveillance
PI	Package Insert
PPBG	Postprandial Blood Glucose
PPPG	Postprandial Plasma Glucose
PRAC	Pharmacovigilance Risk Assessment Committee
SAE	Serious Adverse Event

SADR	Serious Adverse Drug Reaction
SOC	System Organ Class
TC	Technical Complaint
T1DM	Type 1 Diabetes mellitus
T2DM	Type 2 Diabetes mellitus
UTN	Universal Trial Number
WHO	World Health Organization

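### The FPG endpoint pools fasting plasma and fasting blood glucose, and the protocol does not require a record of which was measured

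*Protocol*

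**What the plan says.** Section 7.3 of the protocol sets the endpoint as "Change from baseline in FPG after 1 year of treatment". Sections 8.7.1 and 8.7.2 also name FPG alone as the variable to be summarised, and 8.7.2 adds: "Baseline, end of trial values and change from baseline values will be presented".

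The list of abbreviations in Section 1 has two separate entries, "Fasting Blood Glucose" for FBG and "Fasting Plasma Glucose" for FPG.

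The collection items do not keep them apart. The schedule in 8.3.1 has one combined FPG/FBG row, marked at all four visits, for a value and its date. In 8.4.1 the Visit 1 list asks for the latest such value before insulin degludec was started, and the list for Visits 2 to 4 asks for "Most recent FPG/FBG value and date of measurement since last visit". None of these asks for sample type, or whether the value came from a laboratory or a meter.

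The sources differ slightly by visit. At Visit 1 they are the medical record, recall or a diary if there is one. At Visits 2 to 4 they are the medical record, "patient recall, and/or the patient's SMBG diary". Section 8.3.2 adds no testing, and 8.9 states that there is no control arm.

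**The concern.** The endpoint names one quantity and the data feeding it may be either of two. If whole-blood readings run below plasma readings, a patient with a plasma value at baseline and a blood value at one year shows a fall that did not happen. The reverse order shows a rise that did not happen. With no comparator, a net shift of this kind goes straight into the reported mean change.

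Carrying the last observation forward (8.7.2) adds a route for mixing, because a Visit 2 or Visit 3 value of either type can become the end-of-trial value.

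The analysis plan is not at hand and may deal with pairing or conversion. It can do so only if the sample type was captured, and what is captured follows from the protocol's data list. That makes this a protocol point.

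**Working it through.** The protocol gives no FPG level, standard deviation or expected change, so there is no figure of its own to reproduce. Only the direction and possible size of the effect can be checked.

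**Inputs from the protocol:** FPG/FBG accepted at every visit (8.3.1, 8.4.1); FPG summarised as one variable (8.7.2); no comparator (8.9).

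**Assumed inputs, not in the documents:** a proportional gap *g* by which a blood reading falls below plasma, 0 to 15%; a glucose level of 180 mg/dL; a net share of patients switching type, 20% or 40%.

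**Formula.** Let *B* and *F* be the true mean plasma values at baseline and one year. Let *p0* and *p1* be the shares recorded as whole blood at those times, taken as unrelated to level. Then

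observed mean change = F(1 − g·p1) − B(1 − g·p0) = (F − B) − g(F·p1 − B·p0).

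**1. Switch in one direction only.** With p0 = 0 the error is −g·F·p1, a false fall. With p1 = 0 it is +g·B·p0, a false rise. At a level of 180 mg/dL the size is:

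| Gap *g* | Per switching patient (g × 180) | Mean, net 20% | Mean, net 40% |
|---|---|---|---|
| 0% | 0 | 0 | 0 |
| 5% | 9 | 1.8 | 3.6 |
| 10% | 18 | 3.6 | 7.2 |
| 15% | 27 | 5.4 | 10.8 |

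All entries are in mg/dL. The result scales with the assumed level: at 130 mg/dL, 0.10 × 130 × 0.20 = 2.6 mg/dL.

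**2. Balanced mix.** With p0 = p1 = p the observed change is (F − B)(1 − g·p). If the true change is zero, it stays zero. Take plasma as 1.11 times blood, so g = 1 − 1/1.11 = 0.099, and a true change from 10 to 8 mmol/L. The −2.0 then reads as −1.95 at p = 25% and −1.90 at p = 50%. Individual changes in patients who switch are still off by g times the level in either direction, which adds noise.

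**3. Cross-check on another base.** With the same ratio of 1.11 and a follow-up value of 8 mmol/L, a patient who switches from plasma to blood shows a false fall of 8 × (1 − 1/1.11) = 0.79 mmol/L. The protocol's own pairing of 3.1 mmol/L with 56 mg/dL gives a factor of 56/3.1 = 18.06, so this is about 14 mg/dL. The mean moves by about 2.9 mg/dL at a net 20% and 5.7 mg/dL at a net 40%, inside the ranges above.

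**The case against.** Several objections carry weight.

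- **The CRF is not shown.** Sections 8.3.1 and 8.4.1 list information to gather and are not CRF pages, and 8.6.2 refers to further guidance in the CRF. A reader might infer that sample type is not recorded and that mixed values can never be separated. The documents support only that the protocol does not require the record.
- **The direction is open.** Because an SMBG diary is named only for Visits 2 to 4, a reader might infer a drift from laboratory plasma at baseline to meter readings later, and so a false fall. But Visit 1 also allows recall and a diary, and earlier insulin treatment is listed among prior therapies. Section 8.2.3 excludes only current or past Tresiba users, so home readings can be baseline values too. The diary that 8.4.1 instructs patients to keep covers adverse events, hypoglycaemic episodes and concomitant medications, not fasting glucose.
- **A meter value may already be on a plasma scale.** The protocol defines confirmed hypoglycaemia by a plasma glucose value and collects those episodes from the same sources, the SMBG diary included. If that reading is right, the gap is zero.
- **The endpoint is secondary.** It is summarised descriptively, with no formal test (8.7).

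These points limit the direction, the size and the importance. They do not remove the mismatch between the named endpoint and what is accepted for it. Doubt about the scale of each value is itself a reason to record it.

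**Conclusion.** The point holds as a mismatch between endpoint and data collection. Two measures that the protocol lists separately are accepted interchangeably for an endpoint named after one of them, with no requirement to record which was used.

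A net change of sample type or method between baseline and one year can bias the mean FPG change downwards or upwards. It would be too strong to say that any change of sample type shows up as a treatment effect: only a net switch produces a spurious mean change, and a balanced mix produces noise and slight shrinkage.

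The size rests wholly on assumption. With a 0 to 15% gap, 180 mg/dL and a net 20% switch it is 0 to 5.4 mg/dL. There is no bias if the values are already on a plasma scale, and no spurious change if there is no net switch.

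The primary endpoint (adverse events, 7.3) and the study size, which rests on safety (8.5), are unaffected.

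**What to change.** In 8.3.1 and 8.4.1, require two entries beside each fasting value at Visits 1 to 4: sample type (plasma, whole blood or unknown) and source (laboratory or meter).

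In 8.7.2, state that the change in FPG is summarised in patients whose baseline and one-year values are of the same type and source, and that mixed or unknown pairs are reported separately. A value carried forward should keep its own type and source for this purpose.

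A single conversion factor should not be applied. Values labelled blood may already be on a plasma scale, and converting those would add error.

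The cost is two tick boxes per visit and a short addition to the analysis text, with no extra test and no change to routine care. The downside is fewer pairs in the main FPG summary, more so if many recalled values have to be marked unknown.
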